Cardiac toxicity, including QT prolongation, is considered a safety concern for avapritinib and is classified as an important potential risk in the EU RMP. While non-clinical studies did not show any effects of avapritinib on the cardiovascular system, in clinical Study BLU-285-1101, a small increase in the QTc interval (6.55 ms; 90% CI: 1.80 to 11.296 at 300/400 mg QD clinical dose) that was not clinically relevant was observed in a subset of GIST patients. In addition, the slope of the avapritinib concentration-QTc relationship was very shallow: 0.007 ms per ng/mL (90% CI: 0.003 to 0.012), with a small, non-statistically significant intercept of -0.2 ms (90% CI: -2.26 to 1.89). However, considering the existing potential of mainly multi-target TKIs to cause QT prolongation (Porta-Sanchez et al. 2017) and cardiac toxicity (Orphanos et al. 2009; Chen et al. 2016; Lee et al. 2018; Porta-Sanchez et al. 2017) cardiac toxicity, including QT prolongation is considered an important potential risk associated with avapritinib warranting further evaluation in the post authorisation setting. Therefore, cardiac toxicity, including QT prolongation and associated symptoms such as cardiac arrest, sudden cardiac death, syncope or ventricular arrhythmia are to be closely monitored during the course of this study.

In study BLU-285-1101, 56 patients carried the PDGFRA D842V mutation of whom 17 patients received an avapritinib starting dose <300 mg and 1 patient a starting dose of 600 mg. A total of 38 patients were treated with an avapritinib starting dose of 300 or 400 mg including 28 patients at a starting dose of 300 mg and 10 patients at a starting dose of 400 mg. Of the 56 patients with PDGFRA D842V-mutated GIST, avapritinib was received first-line by 11 patients, second-line by 21 patients, third-line by 10 patients, fourth-line by 6 patients and after at least 4 previous lines of treatment by 8 patients. Of the 11 patients with PDGFRA D842V-mutated GIST received an avapritinib starting dose <300 mg, 4 patients a starting dose of 300 mg and 1 patient a starting dose of 300 mg.

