Baseline and follow-up assessments will be in accordance with local standard medical care. Both prospective and retrospective data collection will be performed in this study. All patients who will initiate or continue treatment with avapritinib after enrolment will have prospective data collection for 24 months on the study. For patients who have received avapritinib prior to enrolment in this study, retrospective data may also be collected (if data are available). Retrospective data collection will be performed at the participating investigator site through extraction of available data from the patient's medical records. The data collection plan is provided in Table 1.

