9.7.2. Statistical Methods

Descriptive analysis:

Demographic and other baseline characteristics collected before or at the time of the first avapritinib dose will be summarised for the SP. Continuous variables will be described (distribution) by their mean, standard deviation, median, extreme values (minimum and maximum) and the number of missing data. Categorical variables will be described using

frequency counts and percentages. Time-to-event data will be summarized by Kaplan-Meier (KM) estimates.

Analysis of the primary endpoint:

The primary endpoint for the study will be to describe AEs during the study period for the SP. Analyses will be conducted for the SP overall and stratified by treatment setting at the first dose of avapritinib and 300 mg dose, Eastern Cooperative Oncology Group (ECOG) performance status and country; feasibility requirements will be described in the SAP.

The study period for the safety analyses is defined as the time from the first dose of avapritinib to the end of follow-up, i.e. at least 24 months, until study discontinuation for any reason, or 30 days after the last dose of avapritinib; whichever comes first.

The following analyses will be performed:

- Number and proportions of patients experiencing an AE during the study period (i.e., from the first dose of avapritinib until the end of follow-up): by SOC (System Organ Class) and PT (Preferred Term) (MedDRA classification), severity, seriousness and relationship to avapritinib, including the description of types, severity and rates of AEs leading to discontinuation or decreased dosing of avapritinib.
- Number and proportions of patients with dose reductions or interruptions, or discontinuing avapritinib treatment due to an AE during the study period: overall and by comorbidity, including the description of types, severity and rates of AEs leading to discontinuation or decreased dosing of avapritinib.
- Incidence rate of patients experiencing an AE, overall and by SOC and PT terms
 - Defined as the number of patients with at least one (specific) AE during follow-up divided by the sum of person-months at risk in the study.
 - The sum of person-months at risk in the study when calculating the overall incidence is defined as the duration of follow-up for patients without AEs plus the duration of follow-up until the date of the first AE for patients with an AE.

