 - The sum of person-months at risk in the study when calculating the incidence for specific AEs is defined as the duration of follow-up for patients without the specific AE plus the duration of follow-up from baseline until the date of the first specific AE for patients with a specific AE, i.e. patients who experience another AE earlier in time will not be censored

Specific safety concerns that will be reported, include but are not limited to:

- Intracranial bleeding (e.g. cerebral haematoma, cerebral haemorrhage, haemorrhage intracranial, subdural haematoma)
- Cognitive effects (e.g. agitation, amnesia, cognitive disorder, confusional state, delirium, dementia, disorientation, encephalopathy, hallucination, memory impairment, mental impairment, mental status changes, mood altered, personality change, psychotic disorder, somnolence, speech disorder)
- Drug-drug interactions with moderate or strong CYP3A4 inhibitors or inducers

- Cardiac toxicity (e.g. electrocardiogram QT interval abnormal, electrocardiogram QT prolonged long QT syndrome, long QT syndrome congenital, torsade de pointes, ventricular tachycardia, cardiac arrest, cardiac death, cardiac fibrillation, cardio-respiratory arrest, electrocardiogram repolarisation abnormality, electrocardiogram U wave inversion, electrocardiogram u wave present, electrocardiogram U-wave abnormality, loss of consciousness, multiple organ dysfunction syndrome, subacute kidney injury, sudden cardiac death, sudden death, syncope, ventricular arrhythmia, ventricular fibrillation, ventricular flutter, and ventricular tachyarrhythmia)
- Embryofoetal toxicity
- Any off-label use in patients with severe hepatic impairment (Child-Pugh class C, i.e. ≥ 10 points, Annex 3)
- Drug-drug interactions with CYP3A4 substrates

Analysis of the secondary endpoints:

Secondary endpoints will be described using the SP. Analyses will be conducted for the SP overall and avapritinib dose 300 mg, and may be stratified by treatment setting at the first dose of avapritinib (i.e. study BLU-285-1101, CUP/EAP, and routine care), Eastern Cooperative Oncology Group (ECOG) performance status and by country if feasible; feasibility requirements will be described in the SAP.

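### QT and other ECG-only terms are rated over all safety follow-up, but the study records no ECGs, so a low rate cannot be told apart from little testing

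*Protocol*

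**What the plan says.** Section 7.1 of the protocol states that "cardiac toxicity, including QT prolongation is considered an important potential risk associated with avapritinib warranting further evaluation" after authorisation. It adds that "cardiac toxicity, including QT prolongation and associated symptoms such as cardiac arrest, sudden cardiac death, syncope or ventricular arrhythmia are to be closely monitored" while the study runs. The abstract makes the same commitment.

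Section 9.7.2 lists cardiac toxicity among the specific safety concerns. The list opens with "electrocardiogram QT interval abnormal, electrocardiogram QT prolonged long QT syndrome" and goes on to a repolarisation abnormality and three U-wave terms. It also contains events that come to notice clinically, such as syncope, cardiac arrest and sudden death.

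The incidence rate in the same section is "Defined as the number of patients with at least one (specific) AE during follow-up divided by the sum of person-months at risk in the study". For a specific event, the person-time "is defined as the duration of follow-up for patients without the specific AE", plus time from baseline to first event for patients who have it. Safety follow-up runs from the first dose to the end of follow-up, study discontinuation, "or 30 days after the last dose of avapritinib; whichever comes first".

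On ascertainment, section 9.1 says: "Baseline and follow-up assessments will be in accordance with local standard medical care". Footnote b of Table 1 allows visits by telehealth. The variable list in section 9.3 and the rows of Table 1 cover adverse events, treatment, concomitant medication, tumour evaluation and survival. Neither contains an ECG item: no done/not done, no date, no QTc.

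**The concern.** Most adverse events can surface through symptoms. A prolonged QT interval, a repolarisation abnormality or a U-wave change is seen only if someone takes an ECG. Under this plan such a finding enters the data only if a site took an ECG in routine care and then reported the result as an adverse event. A patient who never had an ECG contributes full safety follow-up to the denominator as event-free, exactly like a patient with regular normal tracings.

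At stake is the reading of a low or zero QT rate. It could mean that the drug rarely prolongs QT in this setting, or that few ECGs were taken. Section 9.9.1 plans to compare adverse event rates with expected rates from the pooled BLU-285-1101 and BLU-285-1303 trials. Section 7.1 shows that QTc was measured in at least a subset of patients in BLU-285-1101. If ECGs are less frequent in local care, which the protocol does not say, the comparison for these terms would lean towards reassurance.

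**Working it through.** **No plan figure to reproduce.** The protocol gives no expected QT rate and no ECG frequency. Its one sample-size calculation (section 9.5) concerns response rate and has no bearing here.

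**Tracing one event through the document**
- Numerator (9.7.2): patients with a reported specific event. For ECG-only terms this requires an ECG and a report.
- Denominator (9.7.2): all safety follow-up of everyone else. No ECG is required.
- Schedule (9.1, Table 1 footnote b): local care, possibly remote. No ECG is specified.
- Data (9.3, Table 1): no ECG item. Section 9.6 ties the eCRF and chart extraction to the variables in 9.3.

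The numerator is thus conditional on testing, the denominator is not, and the database holds nothing linking the two.

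**Illustration of possible size.** The inputs from the protocol are N = 50 (section 9.5) and 24 months of follow-up (section 9.2.3). Everything else is assumed:
- a share f of patients is tested, independently of QT risk;
- every case among tested patients is found;
- the hazard is constant, with 24-month risk p;
- nobody leaves follow-up early.

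Formulas:
- λ = −ln(1 − p)/24
- detected events D = 50·f·p
- ECG-assessed person-months A = D/λ
- all person-months = A + 50·(1 − f)·24

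For p = 0.10 and f = 0.5:
- λ = 0.10536/24 = 0.00439
- D = 2.5
- A = 2.5/0.00439 = 569.5
- all person-months = 569.5 + 600 = 1169.5
- rate over assessed time = 4.39 per 1000 person-months
- rate by the protocol's definition = 2.5/1169.5 = 2.14 per 1000
- ratio = 0.49

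| Share tested (f) | Protocol rate per 1000 person-months, p = 10% | Ratio to assessed rate, p from 5% to 20% |
|---|---|---|
| 100% | 4.39 | 1.00 |
| 75% | 3.25 | 0.73–0.75 |
| 50% | 2.14 | 0.47–0.49 |
| 25% | 1.06 | 0.23–0.25 |

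**What changes if testing is targeted.** Suppose 50 patients with 5 true cases (10%), of whom 25 have ECGs chosen because of symptoms or risk factors, and 4 cases are found. As simple proportions:
- over all patients: 4/50 = 8%, a shortfall of 20% rather than 50%;
- over tested patients only: 4/25 = 16%, an excess of 60%.

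The shortfall therefore depends on who is tested as well as on how many. Here the two denominators fall on either side of the truth. The protocol supplies neither the share tested nor the reason for testing.

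**The case against.** The person-time denominator is a conventional, general definition for all adverse events in a descriptive, non-interventional study. Other test-dependent events, such as raised bilirubin, share the weakness. The reported concern is cardiac toxicity as a whole, and much of that list needs no study ECG field. Section 9.9.2 admits information bias and calls for sensitivity analyses of the retrospective data. The ENCePP checklist leaves missing-data and misclassification rules to the SAP, section 9.6 leaves further data-collection detail to a data management plan, and safety analyses are stratified by treatment setting.

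Much of this stands, and it limits the point to the ECG-only terms. It does not dispose of it. An ECG that was never taken does not appear as a missing value, and without ECG dates no SAP can state how many patients were assessable. Stratifying by setting may show that rates differ, but cannot separate risk from testing. Raised bilirubin also does not carry the specific monitoring commitment of section 7.1. For another listed concern, CYP3A4 interactions, section 9.3 already tailors collection by giving concomitant medication a special focus.

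Three stronger readings are tempting and are not supported:
- **That the QT rate is understated, by a stated percentage.** The share tested is not in the documents. The proportional relation needs testing to be unrelated to QT risk, which is doubtful in routine care. With near-complete ECG coverage the bias disappears.
- **That tested patients should replace the current denominator.** If ECGs are prompted by symptoms, that rate can be too high. Stopping person-time at the last ECG adds distortion: one early normal tracing would erase nearly all of a long exposure.
- **That a falsely tight confidence limit will be reported.** Zero events would give an exact two-sided 95% upper limit of 1 − 0.025^(1/50) = 7.1% for 50 patients and 1 − 0.025^(1/25) = 13.7% for 25. But section 9.7.2 plans no interval for adverse event rates.

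**Conclusion.** The point holds for the ECG-only terms. The protocol commits to close monitoring of QT prolongation and fixes an incidence rate over all safety follow-up, yet collects nothing that shows who had an ECG. The rate for these terms may be understated unless nearly all patients have on-treatment ECGs. The size is unknown: the figures above rest on assumed testing shares and risks and show only that it could range from nothing to a large part of the rate. The firm conclusion is that the study as written could not tell which applies, so the section 9.9.1 comparison cannot be interpreted for these terms. Syncope, cardiac arrest and sudden death, and hence the overall cardiac rate, are less affected. This is a worthwhile, low-cost improvement. It does not invalidate the primary safety analysis.

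**What to change.** - **Section 9.3 and Table 1:** add, at baseline and on treatment, an item for ECG performed as part of standard care (yes/no), date(s), and QTc if available. No ECG is mandated, so the study stays observational.
- **Section 9.7.2:** keep the current all-follow-up rate. For ECG-only terms, report beside it the number and proportion of patients with an on-treatment ECG and the corresponding person-months. Give the rate among ECG-assessed patients as a supplementary sensitivity figure, with a note that it may be too high if ECGs were prompted by symptoms. Leave clinically apparent cardiac events as they are.
- **Section 9.9.1:** state that the comparison with trial-based expected rates depends, for ECG-only terms, on how often ECGs were taken.
- If the item is not added, the monitoring statement in section 7.1 and the abstract needs to be reconciled with the collection plan.

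The cost is a repeating eCRF item rather than a single field, some abstraction from older charts, and a smaller denominator for the supplementary rate. No patient undergoes an extra procedure.

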9.3. Variables

The data collection plan is outlined in Table 1. Data will be collected prospectively for patients who initiate or continue to receive treatment with avapritinib. Retrospective data collection will be performed when available. All efforts will be made to ensure that the retrospective data of

patients who discontinued avapritinib treatment previously are of good quality and provide sufficient information on the variables required.

Data of interest include the following:

Demographic data and relevant medical history at the time of the first avapritinib dose:

- Age
- Sex
- Height
- Weight
- Race/ethnicity (in accordance with the local regulations)
- ECOG performance status GIST diagnosis (before the first avapritinib dose according to local standard procedures)
 - Date of diagnosis
 - Primary tumor site (e.g. stomach, duodenum, rectum, small intestine)
 - Largest lesion size ($\leq 10 \text{ cm or} > 10 \text{ cm}$)
 - Resectable (yes / no)
 - PDGFRA mutation status
 - Metastatic (yes / no)
 - Location of metastatic site(s)
- Relevant medical and surgical history including comorbidities and previous cancer diagnoses
- Prior imatinib therapy (yes / no)
- Duration of prior imatinib therapy
- Best response to prior imatinib therapy (CR, PR, SD, progressive disease, NE)
- Concomitant medications, with a special focus on CYP3A4 inhibitors/inducers to address the drug-drug interaction risk

The Medical Dictionary for Regulatory Activities (MedDRA) will be used for coding concomitant diseases, and the World Health Organization (WHO) Drug Dictionary for medications.

Avapritinib treatment details from the time of the first dose until 30 days after the last dose:

- Date of treatment initiation
- Primary reason for treatment initiation
- Setting (e.g. trial, CUP, EAP or routine care)
- Treatment schedule (e.g. qd, bid)

- Avapritinib treatment information: dose and dose modifications including date(s)
- Reason for dose modification
- Date of discontinuation or interruption
- Primary reason for discontinuation or interruption
- Reason for initiating further lines of treatment

Efficacy variables:

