11.2. Adverse Event Severity

The investigator will use the following definitions to rate the severity of each recorded event. Severity and seriousness need to be independently assessed by the investigator for each event recorded on the CRF. Severity of events will be classified using NCI CTCAE Version 5.0 (see Table 2; of note a Semi-colon indicates 'or' within the description of the grade).

Grade 1	Mild; asymptomatic or mild symptoms; clinical or diagnostic observations only; intervention not indicated.
Grade 2	Moderate; minimal, local or noninvasive intervention indicated; limiting age appropriate instrumental activities of daily living (ADL).
Grade 3	Severe or medically significant but not immediately life-threatening; hospitalization or prolongation of hospitalization indicated; disabling; limiting self-care ADL.
Grade 4	Life-threatening consequences; urgent intervention indicated.
Grade 5	Death related to AE. ^a

Table 2:Severity rating adverse events

^a Death is not appropriate for some AEs and therefore not an option.

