ANNEX 3. ADDITIONAL INFORMATION

Parameter	1 Point	2 Points	3 Points
Serum albumin (g/dL)	>3.5	2.8 to 3.5	<2.8
Total serum bilirubin (mg/dL)	<2.0	2.0 to 3.0	>3.0
Prothrombin time (sec prolonged)	<4	4 to 6	>6
or international normalised ratio (ratio)	<1.70	1.70 to 2.30	>2.30
Ascites	Absent	Slight	Moderate or Subject on medication(s) to control ascites
Hepatic encephalopathy (see Table 2)	None	Grade 1 or 2	Grade 3 or 4 or subject receiving medication(s) to prevent encephalopathy

Derivation of Child-Pugh Classification Score¹

¹ Adapted from FDA Guidance for Industry. Pharmacokinetics in Patients with Impaired Hepatic Function: Study Design, Data Analysis, and Impact on Dosing and Labeling (FDA 2003).

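### Off-label use in severe hepatic impairment is to be reported by Child-Pugh class C, but neither the class nor any component of the score is among the variables to be collected

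*Protocol*

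**What the plan says.** Section 9.7.2 introduces a list of seven specific safety concerns that will be reported. One is "Any off-label use in patients with severe hepatic impairment", with the criterion given in brackets: "Child-Pugh class C, i.e. ≥ 10 points, Annex 3".

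Annex 3 gives the scoring table. It has five items at 1 to 3 points each: "Serum albumin (g/dL"), "Total serum bilirubin (mg/dL"), "Prothrombin time (sec prolonged") or international normalised ratio, ascites, and encephalopathy. The encephalopathy row reads "Hepatic encephalopathy (see Table 2").

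Section 9.3 lists the data of interest. The nearest entry is "Relevant medical and surgical history including comorbidities and previous cancer diagnoses", recorded as of the first avapritinib dose, with concomitant diseases coded in MedDRA. The rows of Table 1 are consent, eligibility, demographics, medical and surgical history, prior imatinib, concomitant medication, treatment details, progression and response evaluations, telephone contact and adverse events. Section 9.6 states that what is entered in the eCRF or extracted from records is the information set out in Section 9.3.

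The protocol's only Table 2 is in Section 11.2: "Severity of events will be classified using NCI CTCAE Version 5.0 (see Table 2").

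**The concern.** The protocol fixes a numerical rule for a reported safety concern without planning to collect anything the rule needs. An analysis plan cannot repair this, because no derivation or missing-data rule recovers values that were never recorded.

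For a neighbouring concern the protocol does make the match. Drug interactions through CYP3A4 are on the same list, and Section 9.3 and footnote e of Table 1 ask for concomitant medication with particular attention to inhibitors and inducers. Severe hepatic impairment has no corresponding variable.

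At stake is how the count can be read. The study answers a Specific Obligation of the conditional marketing authorisation, so its report goes to the regulator. A count with no stated number of assessed patients does not show whether this use is rare or simply was not looked for.

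**Working it through.** The protocol states no computed figure to reproduce here. The check is whether the class follows from the planned data.

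**Step 1: match the inputs to the collected items.**

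| Needed by Annex 3 | Named in Section 9.3 or Table 1? |
|---|---|
| Serum albumin | No |
| Total bilirubin | No |
| Prothrombin time or INR | No |
| Ascites | Not as a variable; could appear as a comorbidity or adverse event |
| Encephalopathy grade | Not as a variable; could appear as a comorbidity or adverse event |
| Child-Pugh score or class | No |

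**Step 2: what the score can be without laboratory values.** Five items at 1 to 3 points give a range of 5 to 15. With no item known, that whole range is open.

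Now assume, generously, that ascites and encephalopathy are both known and sum to s (2 to 6). The three laboratory items add between 3 × 1 = 3 and 3 × 3 = 9, so the total lies between 3 + s and 9 + s:

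| s | Lowest total | Highest total |
|---|---|---|
| 2 | 5 | 11 |
| 3 | 6 | 12 |
| 4 | 7 | 13 |
| 5 | 8 | 14 |
| 6 | 9 | 15 |

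In every row the lowest total is below 10 and the highest is at least 10. Class C is therefore never established and never excluded; the patient is not evaluable.

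**Step 3: why the denominator matters.** Take the planned minimum of 50 patients (Section 9.5) and suppose the report shows no case. If all 50 had been assessed, the exact upper 95% limits would be:

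- two-sided: 1 − 0.025^(1/50) = 7.1%
- one-sided: 1 − 0.05^(1/50) = 5.8%

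If only m patients had a known class, the two-sided limit is 1 − 0.025^(1/m). The protocol gives no figure for m. For assumed values:

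- m = 25: 1 − 0.025^(1/25) = 13.7%
- m = 10: 1 − 0.025^(1/10) = 30.8%

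The same zero thus carries very different information depending on a number the plan does not ask for. These limits also assume that patients with a known class resemble the rest.

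**Step 4: could such patients be present at all?** The protocol gives no prevalence. For assumed true prevalences of 1%, 2% and 5%, the chance of at least one among 50 is 1 − (1 − p)^50 = 39%, 64% and 92%. The question is not empty over that range.

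**Step 5: the cross-reference.** Annex 3 sends the reader to Table 2 for encephalopathy grades. Table 2 is the general adverse event severity scale, so a site applying Annex 3 would not find the grading there.

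**The case against.** The strongest reply is that the protocol has other routes to these patients. Comorbidities are collected and coded, so a site can record severe hepatic impairment, even with a documented class. All adverse events are collected, and Section 11.1.1 counts an abnormal laboratory finding as a possible one. Section 11.1.3 names off-label use among the conditions in which adverse reactions arise. Section 9.7.2 does not say that the sponsor must compute the score centrally, so an investigator could apply Annex 3 to the patient's records. The eCRF, data management plan and SAP are not shown, and Section 9.3 words its list as what the data include.

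Much of this stands, and it rules out two stronger readings:

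- A reader might infer that no patient can be shown to meet the criterion and that the study will report zero. The documents do not support this. Cases can surface through the routes above, and nothing says an unscored patient is counted as unimpaired. Step 2 shows that class C is not evaluable from the listed items, not that the count is zero.
- A reader might also infer that the score would be contaminated by treatment-related bilirubin rises, reported in the background section at 27% (hyperbilirubinaemia) and 24% (blood bilirubin increased). Those are any-grade adverse event percentages from pooled trials and say nothing about class C. Section 9.3 anchors medical history at the first dose. It is enough that Section 9.7.2 should name that time point for the class as well.

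What the reply does not do is make ascertainment systematic. No section asks a site to score or record the class. Adverse event records carry a CTCAE grade rather than Annex 3 values, and normal or unreported results leave no trace. Section 9.6 ties capture to Section 9.3, so unlisted fields cannot be presumed.

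**Conclusion.** The point holds as a gap in ascertainment. The protocol commits to reporting a safety concern by a fixed threshold, and its listed variables can neither establish nor exclude that threshold for any patient. The likely result is incidental detection and an under-count of unknown size, in which a low or zero figure cannot be separated from absence of assessment.

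The reach is limited. This is one of seven listed concerns in a descriptive study, and it does not touch the overall adverse event proportions, incidence rates, response rate or survival estimates. The conclusion assumes that the eCRF follows Section 9.3, as Section 9.6 says. If the eCRF already holds a Child-Pugh field, only the protocol text needs to catch up. The Table 2 pointer is an editorial error on its own.

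**What to change.** - **Section 9.3 and the Baseline column of Table 1:** add *Child-Pugh class at the first avapritinib dose, from available medical records (components where available; otherwise not available)*.
- **Section 9.7.2:** define the concern by the class at the first dose, and report the number of patients with a known class as the denominator alongside the count.
- **Annex 3:** correct the encephalopathy pointer so that it leads to an encephalopathy grading and not to the adverse event severity table.

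The cost is a baseline entry abstracted from routine records, with no new procedure or visit. Expect a small abstraction effort and some not-available entries, mainly in patients whose data are retrospective; the reported denominator makes those visible.
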